11.4 Enrollment

The point of enrollment is the time at which a subject signs and dates the informed consent form, in accordance with ISO 14155.

Study subjects who are implanted with a permanent Tendyne Mitral Valve will be followed through two years and annually thereafter until study closure. Subjects who have any part of the Tendyne Mitral Valve System introduced into the body, but who do not end up with an implanted Tendyne Mitral Valve will be followed through one month or until any procedure or device related adverse event is resolved, whichever comes later. Subjects will then be exited from the study. Subjects who do not have any part of the Tendyne Mitral Valve System introduced into the body will be exited from the study immediately.

- LV and LA dimensions
- Effective regurgitant orifice area (EROA)
- Mitral valve gradient
- LVEF
- Cardiac output
- LVOT dimensions and gradient

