7.3.1 Primary Safety Objective

To evaluate one month procedural and device safety of the Tendyne Bioprosthetic Mitral Valve System.

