8.5.2 Primary Safety Objective

The primary safety objective is to evaluate one-month procedural and device safety of the Tendyne Bioprosthetic Mitral Valve System.

Subjects included in the analysis: All subjects in whom the Tendyne Mitral Valve System is introduced into the body.

Endpoint: Each of the individual primary safety endpoints will be evaluated (see list in 7.3.2 above). Additionally, composite endpoints may be estimated and evaluated for comparison to the literature.

Data analysis: [REDACTED]

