13.4.1 Valve Placement

1. Ensure that all components are fully de-aired to avoid introducing air emboli into the heart, and continue to flush them with isotonic saline throughout the procedure.
2. Thoroughly rinse the valve with heparinized isotonic saline.
3. Compress and load the valve into the instrument, ensuring that the proud anterior segment is properly aligned with the corresponding marker on the instrument.
4. Determine the proper trajectory from the patient's left ventricular apex to the mitral valve. Puncture the apex and insert a standard .035" guidewire.
5. Ensure a path clear of entanglement in the chordae.
6. Advance the instrument over the guidewire to achieve access to the left ventricle. Further advance it across the mitral valve and into the left atrium.
7. Deploy the valve, while observing the deployment using echo and/or fluoroscopic imaging.
8. Pull the valve proximally into the mitral annulus ensuring that the proud anterior cuff is oriented toward the aortic-mitral continuity.
9. Using echo and/or fluoroscopic imaging, confirm that the valve is oriented correctly.
 - a) If the valve needs to be repositioned, use the instrument to partially recapture the valve, push it up into the left atrium, reorient, and pull it back into position.
 - b) If the valve is the wrong size or otherwise needs to be withdrawn, use the instrument to fully recapture the valve and pull it out through the apical access. If desired, an alternative valve can be deployed.
10. Once proper orientation has been confirmed, adjust tension using the apical pad tool to attain proper seating of the valve for mechanical stability and optimal paravalvular sealing.
11. Once stability is achieved and valve function is determined to be acceptable, remove the instrument and fasten the apical pad to the tether.

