14.2 Scheduled Follow-up Visits

Follow-up data must be documented using the appropriate eCRFs and image data must be submitted in electronic format.

Follow-up visits must occur at the following time points following implantation:

- Pre-discharge Within 24 hours prior to discharge or up to 10 days post-procedure, whichever occurs first
- One month 28 - 40 days
- Three months 90 ± 14 days
- Six months 180 ± 30 days
- One year 365 ± 45 days
- Two years 730 ± 60 days
- Annually thereafter until 5 years.

Subjects who have any part of the Tendyne Mitral Valve System introduced into the body but who do not end up with an implanted Tendyne Mitral Valve only need to be followed through one month or until resolution of any procedure or device related adverse event and then exited from the study. Subjects who are not exposed to the Tendyne Mitral Valve System will be exited from the study immediately. Documentation for subjects exited from the study must be completed using the appropriate CRF.

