17.8 Monitoring

The sponsor will be responsible for monitoring at each site to ensure adequate protection of the rights and safety of study subject, and to verify the quality and integrity of the data collected and submitted. The sponsor will identify and train qualified personnel to conduct monitoring visits. Monitoring will consist of review of subject records, source documents, and other required documentation, including institutional review board/ethics committee approvals and correspondence.

Monitors will conduct site visits to ensure accuracy of data, timeliness of data submission, adequate patient enrollment, compliance with applicable laws and regulations, compliance with this protocol, compliance with the signed investigator agreement, and compliance with institutional review board/ethics committee conditions and guidelines. Any noncompliance with these items that is not adequately addressed by the investigator is cause for the sponsor to put the investigator on probation or withdraw the investigator or site from the study.

The site staff must be available to meet with the monitor or other sponsor representative during monitoring visits. The investigator must allow monitoring by the sponsor and its authorized representatives and any other local governmental body to review the study subjects' medical records, including any test or laboratory data.

Frequency of monitoring will be based on enrollment, study duration, site compliance, and any suspected inconsistency in data that requires investigation.

18 Adverse Event Reporting

An adverse event (AE) is defined as any untoward medical occurrence in a study subject, which does not necessarily have to have a causal relationship with study treatment. An AE can be an unfavorable and unintended sign (including an abnormal laboratory finding), symptom or disease, temporary or permanent, whether or not related to the prosthetic valve implantation or procedure. Refer to 22 for further AE definitions.

Reportable AEs are any that occur from the time a subject becomes enrolled through the subject's exit from the study. Any AE that occurs to any subject during the study must be documented on an AE electronic case report form. Information collected includes: date of onset of first observation; description of the event; seriousness; causal relationship to the device; causal relationship to the procedure; treatment required; and outcome or status of the event.

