## 2.2.4 Performance Endpoint Analyses

#### 2.2.4.1 Technical Success

The primary analysis will be based on the TP population. The definition of technical success is provided in **Section 1.3.2.1**. The composite endpoint will be summarized as the proportion of subjects with technical success at the end of the index procedure. The count and proportion of subjects that meet the criteria of technical success will be summarized along with the 95% exact confidence interval. The individual components of the composite endpoint will also be provided.

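### A procedure abandoned after incision or apical puncture, but before any Tendyne component enters the body, falls outside the Protocol's primary safety population and has no stated 30-day assessment

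*Protocol*

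**What the plan says.** The primary safety objective (Protocol 7.3.1) is "To evaluate one month procedural and device safety of the Tendyne Bioprosthetic Mitral Valve System". The endpoint (7.3.2) combines device success with freedom from device- or procedure-related serious adverse events at 30 days. Its list includes life-threatening bleeding and major vascular complications.

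The analysis population for that objective (Protocol 8.5.2) is "All subjects in whom the Tendyne Mitral Valve System is introduced into the body".

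Two sections set the exit rule. Protocol 11.4: "Subjects who do not have any part of the Tendyne Mitral Valve System introduced into the body will be exited from the study immediately". Protocol 14.2: "Subjects who are not exposed to the Tendyne Mitral Valve System will be exited from the study immediately". By contrast, 11.4 keeps a subject who had a component introduced but no valve implanted for one month, or until related adverse events resolve if that is later.

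The order of the procedure is in Protocol 13.2 to 13.4.1: general anaesthesia, preparation for mini-thoracotomy and for heart catheterization, catheter measurements, then at step 4 of 13.4.1 "Puncture the apex and insert a standard" guidewire. The Tendyne instrument is advanced over that wire at step 6. Section 3.4.3 lists the Tendyne instrument set as an access system and an apical pad tool; its readable text does not mention a guidewire.

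On event capture, Protocol Section 18 says "Reportable AEs are any that occur from the time a subject becomes enrolled through" study exit, and enrolment is at consent (11.4). Section 19.5 sends serious adverse events and deaths to the Clinical Events Committee.

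The SAP runs primary safety (2.2.1) and technical success (2.2.4.1) on the treated population: "The primary analysis will be based on the TP population". The definition of that population (SAP 1.4) is not readable, nor is Protocol 23.6.

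**The concern.** The procedure starts before the device does. A subject can have a thoracotomy and a punctured left ventricle with no Tendyne component in the body. If the team stops there because of bleeding or haemodynamic collapse, that is a procedural harm of the kind the primary safety objective names. As written, the Protocol leaves the subject out of the primary safety population and ends study follow-up at once. A subject stopped one step later is counted and followed for at least a month.

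What is at stake is a one-directional bias. Each omitted failure leaves both numerator and denominator, so the reported safety figure can only look better. There is also a data gap: an event that arises or worsens between exit and day 30 has no stated route into the study record.

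**Working it through.** **1. Which rule applies at each stage**

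| Point at which the case stops | In the 8.5.2 set? | Follow-up stated |
|---|---|---|
| Before the procedure starts | No | Immediate exit |
| After incision or apical puncture, before step 6 | No | Immediate exit |
| After step 6, no valve implanted | Yes | One month, or until related events resolve if later |
| Valve implanted | Yes | Full schedule |

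The second row is the gap. The documents' own definitions place it inside the procedure. Appendix A defines a procedure-related event as one resulting from the implant procedure, with no requirement that a device has entered. SAP 2.2.6 starts device procedure time at first incision and device time at apical penetration.

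A further mismatch: SAP 1.3 has all enrolled subjects followed at 30 days and beyond. With enrolment at consent, that conflicts with the immediate exit in 11.4 and 14.2.

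**2. Effect on the primary safety proportion**

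The plan states no figure to reproduce. Inputs for the illustration are n = 86 (the minimum CE Mark dataset in SAP 1.3), an assumed f failures among those 86, and an assumed k omitted subjects. Each omitted subject fails the composite automatically, because device success requires the intended device to be in place. The failure rate moves from f/n to (f + k)/(n + k).

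| f/86 | k = 1 | k = 3 | k = 5 |
|---|---|---|---|
| 9/86 = 10.5% | 10/87 = 11.5% | 12/89 = 13.5% | 14/91 = 15.4% |
| 17/86 = 19.8% | 18/87 = 20.7% | 20/89 = 22.5% | 22/91 = 24.2% |
| 34/86 = 39.5% | 35/87 = 40.2% | 37/89 = 41.6% | 39/91 = 42.9% |

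The shift for one subject is (n − f)/[n(n + 1)]:

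- f = 9: 77/(86 × 87) = 1.0 percentage point
- f = 17: 69/(86 × 87) = 0.9 points
- f = 34: 52/(86 × 87) = 0.7 points

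For scale, the exact 95% interval for 17/86 is 12.0% to 29.8%, so one or two omitted subjects move the estimate by far less than its sampling uncertainty.

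**3. Effect on 30-day mortality, only if that analysis also omits these subjects**

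SAP 2.2.3.1 gives a 20% performance goal. The analysis text is unreadable, so an exact one-sided 97.5% upper bound is an assumption.

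| Deaths, omitted subject left out | Upper bound | One omitted death added | Upper bound |
|---|---|---|---|
| 6/86 | 14.6% | 7/87 | 15.9% |
| 9/86 | 18.9% | 10/87 | 20.1% |
| 10/86 | 20.4% (already fails) | 11/87 | 21.5% |

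With 8 deaths, adding one gives 9/87, bound 18.7%, still below 20%. One omitted death reverses the result only at exactly 9 deaths. With a 95% bound instead, it does so only at exactly 10 (10/86, 18.9%; 11/87, 20.1%). Starting from 6/86, even three added deaths pass (9/89, 18.3%).

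**The case against.** The strongest reply is that the plan made a consistent choice. Sections 8.5.2, 11.4 and 14.2 all use device introduction as the boundary, which is a recognisable way to define exposure. The SAP population that governs the analysis cannot be read; if it begins at the start of the procedure, the SAP analysis has no such gap. Counting every abandoned case as a composite failure would also mix harmless aborts with real harm, because none has the device in place.

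Three stronger readings are tempting, and the documents do not support them.

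- *These harms go unrecorded.* They do not. Bleeding, collapse or death on the table would happen before exit, so it is reportable and, if serious, goes to the Clinical Events Committee. Disposition counts of enrolled and treated subjects would also show the difference. Section 14.6 requires adverse events to be followed until resolved or stable after withdrawal, although 11.4 and 14.2 do not apply this to the immediate exit.
- *All failed access is excluded.* Only the interval before step 6 is. Once the Tendyne access system enters, access harm counts.
- *Technical success and 30-day mortality are biased, and one death could change the mortality conclusion.* Section 8.5.2 covers primary safety only. The other two depend on text that cannot be read, and the reversal needs an exact death count under an assumed bound. For primary safety, SAP 2.2.1 gives a proportion with an exact interval and no test, so no pass or fail result can change there.

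What stands of the reply is that the effect is probably small and that aborts need a separate line. It does not answer the conflict between an objective covering procedural safety and a population that begins partway through the procedure.

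**Conclusion.** The gap is real in the Protocol as written. A subject whose procedure is abandoned after incision or apical puncture, but before step 6, is outside the primary safety population and has no stated 30-day assessment. Events before exit are recorded and, if serious, adjudicated, but they do not enter the primary safety endpoint. Events after exit have no stated capture.

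The direction is certain: omission favours the device. The size is unknown, because the documents give no expected number of such cases. The figures of 0.7 to 1.0 percentage points per subject rest on 86 subjects and assumed failure rates of about 10% to 40%. Extension to technical success requires that the unreadable treated-population definition follows 8.5.2. Extension to 30-day mortality requires that its unreadable analysis population does so too. This is an inexpensive correction worth making; it is not evidence that the study's conclusions would be wrong.

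**What to change.** - In Protocol 8.5.2, and in the SAP treated-population definition if it matches, define the primary safety set as all subjects in whom the index procedure is started, meaning first skin incision. SAP 2.2.6 already uses that timepoint. Cases stopped after anaesthesia or catheterization but before incision would remain outside this set, and the text should say so.
- Reconcile the exit rules in 11.4 and 14.2, and the follow-up statement in SAP 1.3, with that set. Subjects with a started procedure but no component introduced should have study outcome and adverse event data collected to 30 days, as subjects treated but not implanted do. Immediate exit would then apply only where the procedure never started.
- Report these subjects on a separate line, with their serious adverse events shown apart from the composite, because they fail its device-in-place requirement whether or not they were harmed.
- Show the device-introduced set as a supporting analysis.
- State explicitly which population applies to technical success and to 30-day mortality.

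The cost is wording in a few places, 30-day data on probably a small number of subjects, and safety figures that may look slightly less favourable.

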12.3 Angiography

The subject's coronary artery disease status usually will be known in advance, via a routine diagnostic angiogram done as part of the work-up for cardiac surgery or transcatheter mitral valve repair if clinically indicated. Any stenting treatment should be administered prior to the implantation of the Tendyne Mitral Valve as outlined in the patient eligibility criteria in section 6.4 above. No simultaneous therapeutic procedures should be planned in conjunction with the Tendyne Mitral Valve implantation.

12.3.1 Preoperative Cardiac Computerized Tomography (CT)

Cardiac CT is performed as standard of care for transcatheter valve implantation; therefore, all subjects will have a Cardiac CT performed at baseline to evaluate cardiac dimensions relevant to valve sizing and aid in procedural planning. If a cardiac CT is obtained per non-research clinical practice at any follow-up, it should be provided to the study sponsor. Additionally, a follow-up cardiac CT should be performed at the 1 Month visit, if tolerable by the patient.

12.3.2 Intraoperative Angiography

Subjects will undergo left-heart catheterization with radiographic imaging as per standard-of-care. Imaging will include a left ventriculogram before and after the Tendyne Mitral Valve is placed, for radiographic assessment of LV and mitral valve competence. Care must be taken to minimize the amount of contrast media injected into subjects with compromised renal function. Therefore, left ventriculogram procedures described in this protocol are optional for subjects with stage 3, 4 or 5 chronic kidney disease.

Tendyne will provide specific instruction on intraoperative imaging requirements as part of investigator training.

12.4 Intraoperative Hemodynamic Measurements

Subjects will also undergo right-heart catheterization to measure hemodynamics intraoperatively. Cardiac output (CO), pulmonary arterial (PA), aortic and right arterial (RA) pressures will be measured before and after the Tendyne Mitral Valve is placed via the right heart catheter. LV pressures should be measured via a pigtail catheter. LV pressures should be measured simultaneously and recorded digitally for post-processing analysis if possible.

12.5 History and Physical Examination

At baseline, a standard physical examination and complete medical history must be taken including co-morbidities and co-existing medical conditions; previous cardiovascular and peripheral vascular interventions; symptoms and diagnosis of mitral insufficiency.

12.6 Clinical Status

Clinical status including vital signs and NYHA functional classification must be evaluated at baseline and each scheduled follow-up visit. Vital signs include sitting pulse, sitting blood pressure and body temperature.

12.7 Kansas City Cardiomyopathy Questionnaire (KCCQ)

The KCCQ is a heart failure specific measure of health status and quality of life. It is a 12-item questionnaire that quantifies physical function, symptoms, social function, self-efficacy and quality of life for patients with heart failure. The KCCQ is self-administered and takes approximately 5 minutes to complete. It must be given to subjects at baseline and each scheduled follow-up visit.

12.8 Six-Minute Hall Walk

A six-minute hall walk test must be done at baseline and each scheduled follow-up visit. Subjects will be asked to walk as far as they can for six minutes, and the distance they cover is to be recorded. If a subject has a non-cardiovascular limitation such as an orthopedic restriction or hemiplegia, this must be noted. If a subject is non-ambulatory due to heart failure status, a score of 0 will be recorded.

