Cardiac Index (from ISO 5840-3)

Cardiac output divided by the body surface area in units L/min/m².

Cardiovascular Death (from VARC II)

Any of the following criteria:

- Death due to proximate cardiac cause (e.g., myocardial infarction, cardiac tamponade, worsening heart failure)
- Death caused by non-coronary vascular conditions such as neurological events, pulmonary embolism, ruptured aortic aneurysm, dissecting aneurysm, or other vascular disease
- All procedure-related deaths, including those related to a complication of the procedure or treatment for a complication of the procedure
- All valve-related deaths including structural or non-structural valve dysfunction or other valve-related adverse events
- Sudden or unwitnessed death
- Death of unknown cause

Non-cardiovascular death is any death in which the primary cause of death is clearly related to another condition (e.g., trauma, cancer, suicide).

Causal Relationship (from ISO 5840-3)

Causal relationship is the relationship of the AE to the study device, the implant procedure or the patient's condition. It should be established in line with the following categories:

- **Device-related:** Any AE involving the function of the device, or the presence of the device in the body. Included in this category are events that are directly attributed to the device.
- **Procedure-related:** Any AE that results from the implant procedure. Events in this category are directly related to the general procedural sequelae.
- **Patient condition-related:** Any AE that results from the worsening of a pre-existing condition or cannot be attributed to the device procedure.
- **Unknown:** Any AE that cannot be assigned to any of the above three conditions.

Chronic Kidney Disease, Stages (from National Institute for Health & Clinical Excellence. Clinical Guideline 73: Chronic Kidney Disease, London 2008)

- **Stage 1:** Slightly diminished function; kidney damage with normal or relatively high GFR (≥ 90 mL/min/1.73 m²). Kidney damage is defined as pathological abnormalities or markers of damage, including abnormalities in blood or urine test or imaging studies.
- **Stage 2:** Mild reduction in GFR (60–89 mL/min/1.73 m²) with kidney damage. Kidney damage is defined as pathological abnormalities or markers of damage, including abnormalities in blood or urine test or imaging studies.

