## 1.3.2 Secondary Endpoints

The secondary endpoints are:

- All-cause mortality at 30 days
- Change from baseline in distance walked on the 6MWT at 6 months and 12 months
- Change from baseline in QoL, as measured by KCCQ at 6 months and 12 months
- Change in proportion of NYHA Functional Classification I or II at 12 months

CONFIDENTIAL Page 4 of 15

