# 2.2.3.3 Change from Baseline in Six-Minute Walk Test Distance at 6 Months and 12 Months

To evaluate the benefit of the Tendyne device, the distance walked at 6 months and 12 months as measured by the 6MWT will be compared with those from baseline.

Descriptive statistics will be provided for change from baseline in distance walked on the 6MWT at each follow-up visit. Proportion of subjects with improvement of clinically important differences of at least 24 meters and at least 50 meters (a component of Individual Patient Success, see **Section 1.3.3.3**) at follow-up visit from baseline will also be provided.

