#### 2.5 Handling of Missing Data

**Multiplicity Issues** 

2.6

Analyses will consist of all available data as the full analysis set. Data will only be absent from analyses of study outcomes in the event that they were not available for collection.

In general, missing values in any of the endpoints will not be imputed when summarizing these endpoints using descriptive statistics. All available data collected will be used in the summaries.

CONFIDENTIAL Page 13 of 15

CL 1010439 Statistical Analysis Plan Version A

CONFIDENTIAL Page 14 of 15

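### A subject who cannot walk after a procedural stroke has no defined six-minute walk value, so the stand-alone walk endpoint may lean towards the device.

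*Protocol*

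**What the plan says.** Protocol 12.8 sets the recording rules for the walk test.

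- It applies to everyone: "A six-minute hall walk test must be done at baseline and each scheduled follow-up visit".
- Zero is prescribed for one situation: "If a subject is non-ambulatory due to heart failure status, a score of 0 will be recorded".
- Other limitations are flagged, with no value attached: "If a subject has a non-cardiovascular limitation such as an orthopedic restriction or hemiplegia, this must be noted".

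SAP 1.3.2 lists as a secondary endpoint "Change from baseline in distance walked on the 6MWT at 6 months and 12 months". SAP 2.2.3.3 presents this comparison as evidence of benefit from the device. It adds responder summaries: "Proportion of subjects with improvement of clinically important differences of at least 24 meters", and the same at 50 m.

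SAP 2.5 uses all available data and states that, in general, "missing values in any of the endpoints will not be imputed when summarizing these endpoints using descriptive statistics".

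Disabling stroke is a component of the primary safety endpoint (Protocol 7.3.2, SAP 1.3.1.1). Freedom from it is required for device success (Protocol 7.1.2, SAP 1.3.3.2), and device success is required for individual patient success (Protocol 7.2, SAP 1.3.3.3).

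**The concern.** Section 12.8 names one cause of inability to walk that earns a zero. It places hemiplegia in another category that only has to be noted. Nothing distinguishes a limitation the subject brought into the study from one the procedure produced. Stroke is an anticipated event in Protocol 18.2, so the second kind is foreseeable.

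A coordinator facing a subject who cannot walk after a procedural stroke could reasonably infer that zero is reserved for heart failure and leave the distance blank. The readable missing-data text would then leave that subject out of the mean change, and nothing readable puts the subject back into the responder denominators.

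Such an omission depends on outcome and runs one way: it removes poor results that the treatment itself caused. The study has a single arm and compares subjects with their own baseline, so no control group offsets the effect.

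**Working it through.** **The rule, case by case (Protocol 12.8)**

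| Subject at follow-up | Value under 12.8 |
|---|---|
| Walks, with or without hemiplegia | Distance walked, with a note if limited |
| Cannot walk because of heart failure | 0 m |
| Cannot walk because of a limitation present at baseline | Note required; no value given |
| Cannot walk because of a procedural stroke | Note required; no value given |

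The last two rows are treated alike. For the last row a site could enter 0 m or leave the test missing, and the text does not decide between them.

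**Size**

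The readable text has no effect size, standard deviation or sample size for the walk endpoint, so there is no planned figure to reproduce. What follows shows scale only.

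Inputs from the documents:
- N = 86, the minimum number at 12 months for the CE Mark report (SAP 1.3).
- N = 350, maximum enrolment (Protocol 6.3).

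Assumed inputs, not in the documents:
- 1 to 5% of subjects unable to walk after a procedural stroke, giving k = 1 to 4 of 86, or 4 to 18 of 350.
- Baseline distance b = 200 to 300 m in those subjects.
- Mean change d = 30 to 50 m among subjects with a value.
- Responder proportion p = 40 to 60% among subjects with a value.

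Formulas:
- Mean change if the k subjects are missing: d.
- Mean change if they are scored 0 m: [(N − k)d − kb]/N.
- Difference: k(d + b)/N.
- Responder proportion if missing: p. If counted as non-responders: p(N − k)/N. Difference: pk/N.

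Mean change:
- N = 86, smallest: 1 × (30 + 200)/86 = 2.7 m.
- N = 86, largest: 4 × (50 + 300)/86 = 16.3 m.
- N = 350, smallest: 4 × 230/350 = 2.6 m.
- N = 350, largest: 18 × 350/350 = 18.0 m.

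Responder proportion:
- N = 86: from 0.40 × 1/86 = 0.5 points to 0.60 × 4/86 = 2.8 points.
- N = 350: from 0.40 × 4/350 = 0.5 points to 0.60 × 18/350 = 3.1 points.

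A case inside the range, with N = 86, b = 250 m and d = 40 m: two non-walkers give (84 × 40 − 2 × 250)/86 = 33.3 m, and four give (82 × 40 − 4 × 250)/86 = 26.5 m, against 40 m if they are missing.

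The mean is the more sensitive summary, because each unscored subject hides the loss of a whole baseline distance. In a responder proportion each counts only as one subject.

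**The case against.** The strongest reply is that 12.8 excludes nobody. The test is required at every visit, and a limitation only has to be noted. A reader might infer that a subject disabled by stroke drops out of the walk endpoint by rule. The documents do not say so. A site may enter 0 m, and a hemiplegic subject who can still walk keeps a measured distance. Disabling stroke is defined in Appendix A by the modified Rankin score, not by loss of walking. This stands: the defect is an undefined value, not a prescribed exclusion.

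Second, the harm is captured elsewhere. Disabling stroke fails the primary safety endpoint and device success, and through device success it fails individual patient success, the composite that contains the 50 m criterion. This also stands, and confines the concern to the stand-alone walk summaries.

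Third, a governing rule may sit in text that cannot be read. Protocol 23.10, on missing data, is blacked out, and parts of SAP 2.2.3.3 and 2.5 appear to be missing. An analysis rule there cannot be ruled out. It would not by itself make sites record the same thing under 12.8, which is readable in full.

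Two further inferences are tempting and do not hold.
- Appendix A counts as cardiovascular a "Death caused by non-coronary vascular conditions such as neurological events", which might seem to contradict calling hemiplegia non-cardiovascular. That definition classifies deaths, whereas 12.8 annotates a walk test, so there is no formal conflict.
- The means above should not be read against 24 m. In SAP 2.2.3.3 that figure is a cut-off for the individual subject, and the readable text sets no such threshold for a group mean.

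**Conclusion.** The point holds as a gap in outcome scoring. Section 12.8 gives no value for a subject who cannot walk because of a procedural stroke and does not separate that subject from one with long-standing hemiplegia. If sites leave the value blank, the readable SAP text lets the secondary walk endpoint and both responder proportions omit treatment-caused failures, which favours the device.

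On the assumed inputs, the mean change at N = 86 would be overstated by about 3 to 16 m and the responder proportions by about 0.5 to 3 points. These sizes rest on an assumed frequency of non-walking, assumed baseline and change, every such value being left blank, and the choice of 0 m as the value for these subjects, which is itself a decision about the estimand. The documents do not show that the bias will occur, nor how often such subjects will arise.

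**What to change.** **Protocol 12.8 (or the eCRF instructions).**
- Record 0 m at follow-up when the subject cannot walk because of heart failure, or because of a cardiovascular, device-related or procedure-related event, including stroke, with onset at or after the index procedure. Use the Clinical Events Committee's adjudication where available.
- Record the test as not done, with the reason, only when the inability comes from a limitation present at baseline or from a post-implant event unrelated to the device, the procedure or cardiovascular disease. An unrelated injury after implant then falls in one category only.
- Limit the hemiplegia example to hemiplegia that existed before the implant.

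**SAP 2.2.3.3.**
- Apply the same rule to the mean change.
- Count subjects scored 0 m under the rule as non-responders in the 24 m and 50 m denominators.
- Add a sensitivity analysis that also counts deaths before the visit as non-responders.
- Check that this agrees with any rule in the text that is not public.

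**Cost.** A few sentences across two documents, some rescoring of past visits, and a slightly less favourable walk result. Limitations must already be noted and serious events are already adjudicated, so much of the rescoring should be possible from existing data. Whether the eCRF holds a reason for each test not done should be confirmed.
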